5.3.2. Spleen Volume Evaluable Population at Week XX

The spleen volume evaluable population includes all participants enrolled in the study who received at least 1 dose of study drug (INCB050465 or ruxolitinib), completed a spleen volume baseline assessment, and met at least 1 of the following criteria:

- The participant has Week XX spleen volume assessment.
- The participant has been on study for a minimum of $(7 \times XX + 7)$ days of follow-up.
- The participant has discontinued from treatment on or before Week XX.

5.3.3. Crossover Population

The crossover population includes all participants enrolled in TG10/TG20 who receive at least 1 dose of study drug and later crossover to TG5D.

6. BASELINE, EXPOSURE, AND DISPOSITION VARIABLES AND ANALYSES

The lists of tables, figures, and listings are provided in [Appendix A](#). Sample data displays are provided in a separate document. The lists and the shells are to be used as a guideline. Modifications of the lists or shells that do not otherwise affect the nature of the analysis will not warrant an amendment to the SAP.

6.1. Baseline and Demographics, Physical Characteristics, and Disease History

Data will be summarized overall and by treatment group based on the dose regimen initially assigned for the safety population.

6.1.1. Demographics

The following demographics will be summarized for the safety population by treatment group: age, sex, race, ethnicity, weight (kg), and height.

6.1.2. Baseline Disease Characteristics

The following baseline disease characteristics will be summarized for the safety population by treatment group: disease subtype (PMF, PPV-MF, or PET-MF), baseline TSS, and ECOG performance status reported to IWRS.

6.1.3. Disease History

Date of MF diagnosis and prior bone marrow biopsy data as to fibrosis grade, cellularity, and transfusion history in the prior 12 weeks to enrollment; prior splenic irradiation; and MF prognostic factors including: age > 65 years, presence of constitutional symptoms (weight loss > 10% of the baseline value in the year preceding MF diagnosis, unexplained fever, or excessive night sweats persisting for more than 1 month), marked anemia (Hgb < 10g/dL) at screening, WBC > $25 \times 10^9/L$ at screening, circulating blasts $\geq 1\%$ at screening, and risk level as defined by IWG ([Passamonti et al 2010](#)) will be recorded and summarized for the safety population by treatment group.

Time since diagnosis will be calculated as:

$$\text{Time since diagnosis (years)} = (\text{date of Day 1} - \text{date of diagnosis} + 1) / 365.25$$

6.1.4. Prior Therapy

Number of prior systemic cancer therapy regimens will be summarized for all participants in the safety population by treatment group. Regimen name, component drugs, start and stop date, purpose of the regimen, best response, reason for discontinuation, and date of relapse/progression will be listed.

Number of participants who received prior radiation will be summarized for safety population by treatment group. Radiotherapy type, body site, start and stop date, total dose, and best response will be listed.

Number of participants who had prior surgery or surgical procedure for the malignancies under study will be summarized for the safety population by treatment group. Date and description of the surgery/procedure will be listed.

All treatments for MF, including a complete history of ruxolitinib usage, will be summarized for all participants in the safety population by treatment group.

6.2. Disposition of Participants

The number and percentage of participants who were enrolled, randomized, treated, completed the study, discontinued study treatment with a primary reason for discontinuation, and discontinued from the study with a primary reason for withdrawal will be summarized for all participants in the safety population by treatment group. The number of participants randomized/enrolled by site will also be provided for the safety population by treatment group.

6.3. Protocol Deviations

Protocol deviations recorded on the CRF will be presented in the participant data listings.

6.4. Exposure

For participants in the safety population, exposure to INCB050465 and ruxolitinib will be summarized descriptively by treatment group for initial portion and crossover portion separately as the following:

- **Duration of treatment with study drug (INCB050465):** Date of last dose of INCB050465– date of first dose of INCB050465 + 1
- **Duration of treatment with study drug (ruxolitinib):** Date of last dose of ruxolitinib – date of first dose of ruxolitinib + 1
- **Dose intensity for INCB050465:** Let S be the earliest study day after permanent discontinuation from study, last study visit, or participant death; let D_1, D_2, \dots, D_K , be the K daily doses (mg) of INCB050465 prescribed to the participant accounting for dose increases on study days S_1, S_2, \dots, S_K . Dose intensity for INCB050465 is defined as

$$\text{dose intensity (\%)} = 100 \times [\text{total dose (mg)}] / [\text{assigned dose (mg)}],$$

where a participant's assigned dose of INCB050465 is defined as the sum of the doses prescribed had the participant not experienced dose delays or reductions on each of the S study days. Formally expressed,

$$\text{assigned dose} = \sum_{i=1}^K D_i(t_{i+1} - t_i) \text{ where } t_1 = 1 \text{ and } t_{K+1} = S$$

For example, suppose a participant is assigned INCB050465 10 mg QD, dose escalates per investigator decision to 20 mg QD on Day 19, and discontinues on Day 31. The assigned dose of INCB050465 for the participant in question is

$$\text{assigned dose} = (19 - 1) \times 10 + (31 - 19) \times 20 = 420 \text{ mg.}$$

- **Dose intensity for ruxolitinib:** Let S be the earliest study day after permanent discontinuation from study, last study visit, or participant death; let D_1, D_2, \dots, D_K , be the K daily doses (mg) of ruxolitinib prescribed to the participant accounting for dose increases on study days S_1, S_2, \dots, S_K . Dose intensity for ruxolitinib is defined as

$$\text{dose intensity (\%)} = 100 \times [\text{total dose(mg)}]/[\text{assigned dose (mg)}],$$

where a participant's assigned dose of ruxolitinib is defined as the sum of the doses prescribed had the participant not experienced dose delays or reductions on each of the S study days. Formally expressed,

$$\text{assigned dose} = \sum_{i=1}^K D_i(t_{i+1} - t_i) \text{ where } t_1 = 1 \text{ and } t_{K+1} = S$$

For example, suppose a participant is assigned ruxolitinib 10 mg BID, dose de-escalates per investigator decision to 5 mg BID on Day 19, and discontinues on Day 31. The assigned dose of ruxolitinib for the participant in question is

$$\text{assigned dose} = (19 - 1) \times 20 + (31 - 19) \times 10 = 480 \text{ mg.}$$

- **Average daily dose of INCB050465 (mg/day):** total actual INCB050465 dose taken (mg) / duration of treatment with INCB050465 (days).
- **Average daily dose of ruxolitinib (mg/day):** total actual ruxolitinib dose taken (mg) / duration of treatment with ruxolitinib (days).

Total actual dose taken will be calculated based on the information entered on the drug accountability CRF.

- **INCB050465 dose modifications:** Number of participants who had INCB050465 dose reduction, escalation, and interruption will be summarized.
- **Ruxolitinib dose modifications:** Number of participants who had ruxolitinib dose reduction, escalation, and interruption will be summarized.
- **Starting dose of ruxolitinib:** The starting dose of ruxolitinib at the time of the first dose of INCB050465 will be summarized.

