5.2. Treatment Groups

As the study was terminated early, participants from all parts will be combined. Data will be summarized overall and by treatment group based on the dose regimen initially assigned in the initial portion:

- TG10: Ruxolitinib at stable dose plus INCB050465 10 mg QD for 8 weeks followed by 10 mg once weekly.
- TG20: Ruxolitinib at stable dose plus INCB050465 20 mg QD for 8 weeks followed by 20 mg once weekly.
- TG5, TG5I/M: Ruxolitinib at stable dose plus INCB050465 20 mg QD for 8 weeks followed by 5 mg QD.
- TG5D: Ruxolitinib at stable dose plus INCB050465 5 mg QD from Day 1 until EOT visit.

Note that TG5I/M in Part 4 is identical to TG5 from Part 3; participants from these 2 groups will be combined in the final analysis.

The crossover participants will be summarized in the initial portion from the date of randomization to the date before crossover.

In the crossover portion, the crossover participants will be summarized in TG5D from the date of crossover to the end of study. Only the crossover participants will be summarized in the crossover portion. Participants in TG5 (TG5I/M) and TG5D and the participants in TG10 or TG20 who do not meet the crossover criteria will remain in the treatment group initially assigned in the initial portion.

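### SAP 6.4 defines dose intensity inconsistently; read literally, planned step-downs, weekly phases and days after the last dose count as under-dosing

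*SAP*

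**What the plan says.** SAP 6.4 defines dose intensity as 100 times total dose over assigned dose. For INCB050465 the assigned dose is built from K daily doses "prescribed to the participant accounting for dose increases on study days", and in words it is "defined as the sum of the doses prescribed had the participant not experienced dose delays or reductions on each of the S study days". The sum stops at S, which the SAP introduces thus: "Let S be the earliest study day after permanent discontinuation from study, last study visit, or participant death". The ruxolitinib definition uses the same wording.

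Each definition has a worked example. In the INCB050465 one, the participant starts at 10 mg daily, then "dose escalates per investigator decision to 20 mg QD on Day 19, and discontinues on Day 31". In the ruxolitinib one, the participant starts at 10 mg BID, then "dose de-escalates per investigator decision to 5 mg BID on Day 19, and discontinues on Day 31".

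Three of the four treatment groups in SAP 5.2 have a planned fall in dose or frequency. TG5 and TG5I/M receive "Ruxolitinib at stable dose plus INCB050465 20 mg QD for 8 weeks followed by 5 mg QD". TG20 receives "Ruxolitinib at stable dose plus INCB050465 20 mg QD for 8 weeks followed by 20 mg once weekly", and TG10 has the same pattern at 10 mg. Only TG5D stays on one daily dose throughout. SAP 6.4 does not say how a scheduled decrease or a weekly dose enters the sum.

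**The concern.** A programmer who follows the words of the definition would hold the denominator at the starting daily dose after Week 8, because a scheduled step-down is not an increase. The sum would also continue after the last dose: Protocol 5.6.2 says that stopping study treatment is not study withdrawal, and Protocol 4.4 places a follow-up visit 30 to 35 days after the last dose.

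The result would be a gap in the exposure tables between TG5D and TG5I/M, the two groups of the primary comparison, that comes from the formula and not from how either regimen was tolerated. A programmer who follows the ruxolitinib example would get different numbers from the same data.

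**Working it through.** **Formula (SAP 6.4).** Assigned dose = sum of D_i × (t_{i+1} − t_i), with t_1 = 1 and t_{K+1} = S.

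**The plan's own examples.**
- INCB050465: (19 − 1) × 10 + (31 − 19) × 20 = 180 + 240 = 420 mg. This matches the SAP.
- Ruxolitinib, as printed: (19 − 1) × 20 + (31 − 19) × 10 = 360 + 120 = 480 mg. This also matches the SAP.
- Ruxolitinib, by the written definition (no reductions): (31 − 1) × 20 = 600 mg. This does not match.

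A participant in the ruxolitinib example who took every prescribed tablet would score 480/480 = 100% by the example and 480/600 = 80% by the definition.

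**Planned decreases.** Inputs: regimens from SAP 5.2, perfect compliance, no crossover, 168 days on treatment (56 daily-phase days, then 112 days or 16 weekly doses), S the day after the last dosing day.

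| Group | Dose taken (mg) | Assigned, literal (mg) | Literal | Assigned, by schedule (mg) | By schedule |
|---|---|---|---|---|---|
| TG5D | 168×5 = 840 | 840 | 100% | 840 | 100% |
| TG5I/M | 56×20 + 112×5 = 1680 | 168×20 = 3360 | 50.0% | 1680 | 100% |
| TG20 | 56×20 + 16×20 = 1440 | 168×20 = 3360 | 42.9% | 1440 | 100% |
| TG10 | 56×10 + 16×10 = 720 | 168×10 = 1680 | 42.9% | 720 | 100% |

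The literal figures depend on time on treatment. TG5I/M is at 100% to Week 8, 75.0% at Week 12 (1260/1680) and 37.5% at Week 48 (2520/6720). TG20 is at 71.4% at Week 12 (1200/1680) and 28.6% at Week 48 (1920/6720).

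**End point S alone.** TG5D has no step-down, so it isolates this effect. If the last assigned day is the follow-up visit, dose intensity = days treated / (days treated + 30 to 35).
- After 8 weeks: 56/86 to 56/91 = 65.1% to 61.5%.
- After 12 weeks: 84/114 to 84/119 = 73.7% to 70.6%.
- After 24 weeks: 168/198 to 168/203 = 84.8% to 82.8%.
- After 48 weeks: 336/366 to 336/371 = 91.8% to 90.6%.

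**Both together.** TG5I/M after 24 weeks plus 30 to 35 days:
- Literal: 1680/(198×20) to 1680/(203×20) = 42.4% to 41.4%.
- By schedule: 1680/(1680 + 30×5) to 1680/(1680 + 35×5) = 91.8% to 90.6%.

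So the tail after the last dose remains even when the step-down is handled correctly.

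**The case against.** The strongest reply is that the increases-only rule is not the SAP's only position. The ruxolitinib example lowers the denominator under the same words. The worded definition can also be read to include the schedule: without any delay or toxicity reduction, a TG5I/M participant would still be prescribed 5 mg after Week 8. Protocol 4.1 calls that change a switch to a maintenance dose, and in Protocol 5.5.6 a dose reduction is a toxicity step. This stands. A reader might infer that compliant participants will certainly appear heavily under-dosed; the documents support that only on one reading.

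It does not rescue the text. Protocol 1.7 and 1.8.3 describe the same changes as a decrease and a reduction, so the literal reading is natural too. Following the ruxolitinib example would make investigator de-escalations lower the denominator, so unplanned reductions would disappear from dose intensity. Neither reading, as written, separates planned from unplanned decreases or says how a weekly dose enters a sum of daily doses.

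On S, the INCB050465 example ends at discontinuation with no follow-up tail, and S is the earliest of three events, not simply the last visit. That is fair. But the listed events do not include stopping treatment. A reader might also infer heavy under-dosing for everyone off treatment; the effect is large only after short treatment and moderate at 24 weeks.

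Finally, a reader might take dose intensity to be the main tolerability measure. No section says so. Safety and tolerability are assessed through adverse events and laboratory changes (SAP 2.3.2), and SAP 8.2.5 tabulates interruptions, reductions and discontinuations because of adverse events for each drug.

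**Conclusion.** The point holds as an inconsistent definition that gives wrong values when read literally. With perfect compliance to Week 24 and no crossover, the three groups with planned decreases can score anywhere from 43% to 100% depending on the reading: TG5I/M 50% or 100%, TG20 and TG10 43% or 100%. The 100% figures assume that the schedule sets the denominator and that weekly doses are counted weekly.

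The contradiction between 480 mg and 600 mg does not depend on any assumption. The end-point fault is present on either reading; its size, 71 to 74% after 12 weeks and 83 to 85% after 24 weeks in TG5D, assumes that S falls at the follow-up visit.

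The consequence is limited to a descriptive exposure summary. INCB050465 compliance (SAP 6.5) divides by a prescribed dose that follows all modifications. Average daily dose divides by the time from first to last dose. Neither is affected, nor is the primary analysis. The change should still be made, because the misleading contrast would fall between the groups that the trial compares.

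**What to change.** In SAP 6.4:

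- Define the INCB050465 assigned dose on each day by the participant's assigned regimen as written in SAP 5.2, with weekly doses counted weekly, plus any escalations. Only unplanned delays and reductions then lower dose intensity.
- End the sum at permanent discontinuation of the drug concerned. For the initial portion of a crossover participant, end it the day before crossover, as SAP 3.5 already does for that portion.
- Reconcile the ruxolitinib example with its definition, and use one notation for the change days, which are S_i in the text and t_i in the formula.
- Add a worked example with a scheduled step-down and one with a weekly phase.

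With these changes a fully compliant participant scores 100% in every group: 1680/1680 mg in TG5I/M, 1440/1440 mg in TG20, 720/720 mg in TG10 and 840/840 mg in TG5D at Week 24. The cost is SAP wording and programming of the exposure tables; trial conduct and data collection do not change.

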### **5.5.8. Criteria and Procedures for Dose Interruptions or Adjustments for Ruxolitinib**

**Dose modifications of ruxolitinib because of toxicity are not required unless INCB050465 modifications/interruptions have been first implemented for 14 days with no improvement in toxicity grade.** In such a case, a brief interruption or dose decrease may be needed. Dose interruptions and modifications for ruxolitinib because of hematologic toxicity that continues after interruption of INCB050465 are shown in [Table 7](#).

**Table 7: Dose Reductions/Interruptions and Restarts for Hematologic Toxicities That Persist for > 14 Days After Interruption of INCB050465**

ANC ( $\times 10^9/L$ )		Platelet Count ( $\times 10^9/L$ )	Dose of Study Drug (Ruxolitinib)		
Value	CTCAE Grade		Value	CTCAE Grade	Dose of Study Drug (Ruxolitinib)
0.5 to < 1.0	3	or	25 to < 50	3	In case of hematological toxicity, INCB050465 will be the first drug to be interrupted, as this is the newly added agent. If the Grade 3 cytopenia persists > 14 days after interrupting INCB050465 or if the primary investigator deems that earlier ruxolitinib interruption is necessary, then ruxolitinib will be interrupted until the toxicity is resolved to $\leq$ Grade 1 or pretherapy baseline and then restarted at the current dose. If a Grade 3 event recurs and persists > 14 days after interrupting INCB050465 or if the primary investigator deems that earlier ruxolitinib interruption is necessary, then ruxolitinib will be interrupted, and the restart dose (after recovery to $\leq$ Grade 1 or pretherapy baseline) of ruxolitinib will be 1 dose level (5 mg BID less) lower than the dose that resulted in the cytopenia.

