6.5. Study Drug Compliance

The participants in the safety population by treatment group for the initial portion and crossover portion separately, overall compliance (%) for INCB050465 will be calculated as

$$\text{compliance (\%)} = 100 \times [\text{total dose actually taken}] / [\text{total prescribed dose}].$$

The total prescribed dose is defined as the sum of the doses prescribed by the investigator accounting for dose modifications.

The total actual dose taken will be calculated based on information entered on the drug accountability CRF. If there is dispensed drug that have not been returned yet, the actual dose taken starting from the dispense date of the unreturned drug will be imputed by the dose taken as reported on the dosing CRF.

Ruxolitinib will be commercially supplied, and the compliance of ruxolitinib will not be calculated.

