3.1 Dose Exposure			
3.1.1.1	Summary of Study Drug Exposure and Compliance to INCB050465	Safety Initial Portion	X
3.1.1.2	Summary of Study Drug Exposure and Compliance to INCB050465	Safety Crossover Portion	X
3.1.2.1	Summary of Study Drug Exposure and Compliance to Ruxolitinib	Safety Initial Portion	X
3.1.2.2	Summary of Study Drug Exposure and Compliance to Ruxolitinib	Safety Crossover Portion	X

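### The ruxolitinib dose-intensity example in SAP 6.4 contradicts its own definition: it gives an assigned dose of 480 mg where the definition gives 600 mg

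*SAP*

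**What the plan says.** SAP Section 6.4 (Exposure) defines ruxolitinib dose intensity as 100 times the total dose divided by the assigned dose. It states the rule for the denominator in two ways:

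- In words, a participant's "assigned dose of ruxolitinib is defined as the sum of the doses prescribed had the participant not experienced dose delays or reductions".
- In the notation, the D values are the "daily doses (mg) of ruxolitinib prescribed to the participant accounting for dose increases on study days", so the sequence moves only when the dose goes up.

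The same definition is given for INCB050465. Its example is a participant on 10 mg QD whose "dose escalates per investigator decision to 20 mg QD on Day 19" and who stops on Day 31, with an assigned dose of 420 mg.

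The ruxolitinib example concerns a participant "assigned ruxolitinib 10 mg BID, dose de-escalates per investigator decision to 5 mg BID on Day 19, and discontinues on Day 31". The SAP gives this participant an assigned dose of 480 mg.

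Section 6.5 says that "the compliance of ruxolitinib will not be calculated". Tables 3.1.2.1 and 3.1.2.2 in Appendix A nevertheless carry the title "Summary of Study Drug Exposure and Compliance to Ruxolitinib".

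**The concern.** The example applies the summation to a dose cut, which the definition says to disregard. One programmer coding from the definition and another coding from the example would report different ruxolitinib dose intensities in Tables 3.1.2.1 and 3.1.2.2, each with support from the same section.

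If the example is followed, a reduction lowers numerator and denominator together and drops out of the statistic. Only interruptions and missed doses would still lower it. The result then resembles a compliance measure, which Section 6.5 rules out for ruxolitinib. A reader of the tables would also not see from this statistic that background ruxolitinib had been cut.

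Reductions can be expected under the protocol. In Table 7 (Section 5.5.8), once the stated conditions are met, "then ruxolitinib will be interrupted until the toxicity is resolved to" the required level. Recurrent persistent Grade 3 cytopenia, persistent Grade 4 cytopenia and neutropenic fever then lead to restart one level (5 mg BID) lower. Section 5.7.3 also allows a change from BID to QD dosing when a moderate CYP3A4 inhibitor is used.

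**Working it through.** **Inputs (SAP 6.4).** The assigned dose is the sum of D_i(t_{i+1} - t_i), with t_1 = 1 and the last t equal to S. In both examples S = 31, so there are 30 dosing days: 18 before Day 19 and 12 from Day 19 on. Ruxolitinib 10 mg BID is 20 mg/day; 5 mg BID is 10 mg/day.

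**The SAP's own figures**

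- INCB050465: (19 - 1) x 10 + (31 - 19) x 20 = 180 + 240 = 420 mg. This reproduces the SAP and agrees with the definition, because the change is an increase.
- Ruxolitinib: (19 - 1) x 20 + (31 - 19) x 10 = 360 + 120 = 480 mg. This also reproduces the SAP. The arithmetic is right; the step down on Day 19 is what the definition excludes.

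**The ruxolitinib case by the definition.** There is no increase, so there is a single dose level of 20 mg/day: (31 - 1) x 20 = 600 mg.

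**Effect on dose intensity.** The first row is the SAP's participant with every prescribed dose taken. The other rows are assumed variations on it.

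| Course | Dose taken (mg) | By the example | By the definition |
|---|---|---|---|
| Cut to 5 mg BID on Day 19 | 18 x 20 + 12 x 10 = 480 | 480/480 = 100% | 480/600 = 80% |
| Cut on Day 19, back to 10 mg BID on Day 25 | 18 x 20 + 6 x 10 + 6 x 20 = 540 | 540/540 = 100% | 540/600 = 90% |
| Interrupted Days 12 to 18, restart at 5 mg BID | 11 x 20 + 12 x 10 = 340 | 340/480 = 70.8% | 340/600 = 56.7% |
| Interrupted Days 12 to 18, restart at 10 mg BID | 11 x 20 + 12 x 20 = 460 | 460/600 = 76.7% | 460/600 = 76.7% |

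The two versions differ only when the dose is reduced. An interruption alone gives the same answer either way.

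**Day-count check.** If Day 31 were counted as a dosing day, the definition would give 490/620 = 79%. The SAP's formula does not count it, and the gap is essentially the same.

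**What other outputs show.** Average daily dose for the SAP's participant is 480/30 = 16 mg/day, taking Day 1 as the first counted dose, against a starting dose of 20 mg/day. Neither figure depends on the assigned dose.

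**The case against.** **The rule is clear and the example is only an illustration.** The definition is given in words and in notation, and is repeated for INCB050465 with an example that fits. A careful programmer would let it govern. That is reasonable, but worked examples are often what gets coded, and nothing in the SAP says the definition takes precedence.

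**A de-escalation decided by the investigator might not count as a reduction.** The text does not support this. Section 6.4 lets the dose sequence change for increases only. When it lists ruxolitinib dose modifications it names reduction, escalation and interruption, and a move from 10 mg BID to 5 mg BID can only be the first. The INCB050465 example also attributes its change to the investigator, so that phrase marks no separate category. A denominator that follows modifications does exist, in Section 6.5, but it belongs to INCB050465 compliance.

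**The derivation may be settled elsewhere.** Appendix A lists these as standard tables following a separate set of conventions, and the shells are in another document. Neither was available, so divergent tables are a risk and not a certainty. The SAP would still contradict itself.

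**The practical effect may be small.** This stands. Under Protocol 5.5.8, ruxolitinib changes for toxicity normally come only after 14 days of INCB050465 modification or interruption without improvement, and a first Grade 3 cytopenia restarts at the current dose. An interruption beginning on Day 12 therefore fits only where the investigator judges that ruxolitinib must be stopped earlier, so the interruption rows above show direction and do not represent a typical course. The compliance-type table title likewise adds no separate error.

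**Conclusion.** The ruxolitinib example in SAP 6.4 is wrong as written. By the section's own definition the assigned dose is 600 mg, not 480 mg. For the SAP's participant, with all prescribed doses taken, that is a dose intensity of 80% instead of 100%.

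The point is minor. It affects one descriptive exposure statistic, and no hypothesis test or efficacy result depends on it. Lost exposure would still be visible elsewhere: "The starting dose of ruxolitinib at the time of the first dose of INCB050465 will be summarized", and average daily dose and counts of dose modifications are defined separately. The 20-point gap belongs to the SAP's illustrative numbers. The effect on the reported tables depends on how many participants had ruxolitinib reductions, by how much and for how long, and the documents do not give this.

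**What to change.** In SAP 6.4, replace the ruxolitinib calculation with (31 - 1) x 20 = 600 mg. Add one sentence stating that a return to the earlier dose after a reduction does not change the assigned dose. This arguably follows from the definition already, but it stops such a return being coded as a dose increase.

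The cost is one corrected figure and one sentence in the SAP, with no protocol change, new data, added procedures or additional patients.
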